## 11.3 Follow-up (FU) data

### 11.3.1 Primary Endpoint at year 3 follow-up

Primary endpoint is the proportion of participants with sustained virologic suppression, defined as HIV-RNA <50 copies/mL or if between 50-200 copies/mL with a subsequent next available measurement\* (within 120 days) <50 copies/mL at year 3 follow-up.

(\*Any subsequent measurement will be accepted as a consecutive measurement as long as measured no later than 120 days after the initial measurement. If no subsequent HIV-RNA measurement is performed within 120 days this is scored as a confirmed HIV-RNA ≥200 copies/mL)

Listing for participants excluded for primary endpoint analyses for the following reason:

- Lost to follow-up

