3.4.1 Primary Endpoint

Proportion of patients with sustained virologic suppression, defined as VL < 50 c/ml or if between 50-200 c/ml with a subsequent next available measurement* (within 120 days) < 50 c/ml at year 1, 2, and 3.

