## 10 Statistical Methods

### 10.1 Definition of analysis time window

### 10.2 Year 1, 2, and 3 follow-up windows

**Year 1 follow-up window** is defined as 9 to 15 months [275 days; 457 days] after the therapy start. This window applies to all variables incl. patient reported outcomes.

Rule for two or more assessments in the time window:

The closest available assessment to year 1 (365 days) after therapy start while the participant is on treatment and continued on study within the time window.

**Year 2 follow-up window** is defined as 21 to 27 months [640 days; 822 days] after the therapy start. This window applies to all variables incl. patient reported outcomes.

Rule for two or more assessments in the time window:

The closest available assessment to year 2 (730 days) after therapy start while the participant is on treatment and continued on study within the time window.

**Year 3 follow-up window** is defined as 33 to 39 months [1005 days; 1185 days] after the therapy start. This window applies to all variables incl. patient reported outcomes.

Rule for two or more assessments in the time window:

The closest available assessment to year 3 (1095 days) after therapy start while the participant is on treatment and continued on study within the time window.

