### 11.3.2 Secondary Endpoints (EPs) (analyzed at years 1, 2 and 3 follow-up, unless otherwise stated)

- Primary endpoint is the proportion of participants with sustained virologic suppression, defined as HIV-RNA <50 copies/mL or if between 50-200 copies/mL with a subsequent next available measurement\* (within 120 days) <50 copies/mL at years 1 and 2 follow-up
- Proportion of participants with HIV-RNA <50 copies/mL at years 1, 2 and 3 follow-up
- Proportion of participants with low level viremia, defined as a HIV-RNA measurement ≥50 copies/mL and <200 copies/mL at years 1, 2 and 3 follow-up
- Proportion of participants with virologic rebound, defined as two consecutive HIV-RNA measurements ≥200 copies/mL from baseline until year 3 follow-up
- Proportion of participants with two consecutive measurements of ≥200 copies/mL, or treatment switch due to virologic failure or due to intolerance as determined at the discretion of the physician from baseline until year 3 follow-up
- Number of HIV monitoring measures (HIV-RNA measurements) [normalized to participant years] from baseline until year 3 follow-up
- Number and frequency of serious adverse events (SAEs) from baseline until year 3 follow-up [normalized to participant years] (see 11.3.10)
- Number and frequency of adverse drug reactions (ADRs) from baseline until year 3 follow-up [normalized to participant years] (see 11.3.10)
- Adherence to therapy [refers to missed monthly doses] at years 1, 2 and 3 follow-up (see 11.3.4)
- Change in lipid laboratory values at years 1, 2 and 3 follow-up (see 11.3.8.3)
- Change in treatment satisfaction [HIV Treatment Satisfaction questionnaire] at years 1, 2 and 3 follow-up (see 11.3.12.2)
- Change in symptom distress [HIV Symptom Distress Module questionnaire] at years 1, 2 and 3 follow-up (see 11.3.12.1)
- Reason for switch to DTG+RPV (see 11.3.5)
- Referral to other medical specialist from baseline until year 3 follow-up (see 11.3.7)
- Proportion of participants with resistance testing from baseline until year 3 follow-up
- Listing of detected resistance-associated mutations from baseline until year 3 follow-up
  - Listing of new (emerging) resistance-associated mutations, incl. resistance-associated mutations detected prior to treatment with DTG+RPV and last HIV-RNA

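### The SAP cuts the primary time points from years 1, 2 and 3 to year 3 without giving a reason, and its 'sustained' suppression is a year-3 status that ignores earlier confirmed rebound

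*SAP*

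**What the plan says.** **Time points.** Protocol 3.4.1 counts a patient as a success if the viral load is below 50, or if it is 50-200 "with a subsequent next available measurement* (within 120 days) < 50 c/ml at year 1, 2, and 3". It does not say whether the three years form one joint criterion or three separate proportions. SAP 11.3.1 keeps the definition ("Primary endpoint is the proportion of participants with sustained virologic suppression, defined as HIV-RNA <50 copies/mL") but ends it with "<50 copies/mL at year 3 follow-up". SAP 11.3.2 lists the same definition, "<50 copies/mL at years 1 and 2 follow-up", among the secondary endpoints.

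**Which value counts.** SAP 10.2 selects, within days 1005 to 1185, "The closest available assessment to year 3 (1095 days) after therapy start while the participant is on treatment and continued on study". Under SAP 11.3.1 a value of 50-200 copies/mL is settled by the next one within 120 days, so one or two measurements decide the status.

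**Rebound.** SAP 11.3.2 has a separate secondary endpoint, "two consecutive HIV-RNA measurements ≥200 copies/mL from baseline until year 3 follow-up". Protocol 3.4.2 also keeps rebound as a secondary endpoint. Neither document makes it a failure of the primary endpoint.

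**Objective.** Protocol 2.1 and SAP 6.1 both state the primary objective as the sustainability of suppression.

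**The concern.** There are two linked problems.

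First, the protocol and the SAP disagree on when the primary endpoint is assessed, and the SAP does not say why. The SAP is also unclear within itself. The years 1 and 2 item in SAP 11.3.2 still opens by calling itself the primary endpoint. In SAP 11.1.1 the asterisk that marks the primary endpoint stands against virologic response at all three years.

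Second, the word 'sustained' promises a statement about the whole period, while the measure describes one point in it. Someone who rebounded in year 1 or 2, stayed on treatment and was suppressed again near day 1095 enters the numerator as sustained. A reader of the final report would take the headline proportion as evidence of durability. No planned output shows how many of those counted had lost suppression on the way.

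**Working it through.** **1. The plan's own figure.** Protocol 3.5 asks for a 95% interval of total width 0.10 at 90%. The exact (Clopper-Pearson) width is 0.1001 at N = 157 and 0.0997 at N = 158, so 158 reproduces. With 30% dropout, 158 / 0.70 = 225.7, which rounds up to 226 and also reproduces. Both figures rest on a single 90% proportion at the end of three years, and this point does not disturb them.

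**2. Joint or separate matters.** If 90% of the same participants are suppressed at each year, the share suppressed at all three lies between 1 - 3 × 0.10 = 70% (no overlap of failures) and 90% (complete overlap). The protocol's wording allows either a year-by-year figure of 90% or a joint figure anywhere in that range.

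**3. Gaps between windows.** The SAP 10.2 windows are days 275-457, 640-822 and 1005-1185. The days lying strictly between them number 640 - 457 - 1 = 182 and 1005 - 822 - 1 = 182. Protocol 3.3.1 expects routine follow-up every 2-4 months, so a rebound and a return to suppression can both fall inside one gap.

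**4. Two hypothetical participants, both on treatment and on study throughout.**
- A: at least 200 at the value nearest day 365 and at the next one; below 50 nearest days 730 and 1095.
- B: below 50 nearest days 365, 730 and 1095; at least 200 on days 500 and 560; below 50 on day 620.

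| Reading | A | B |
|---|---|---|
| SAP 11.3.1, year 3 | sustained | sustained |
| Protocol 3.4.1, separate proportions, year-3 figure | sustained | sustained |
| Protocol 3.4.1, joint over years 1, 2, 3 | not sustained | sustained |
| Confirmed rebound, SAP 11.3.2 | yes | yes |

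The SAP's narrowing changes A's result only on the joint reading. It does not change B's on any reading.

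**5. What the planned outputs can show.** Among n evaluable participants, let S be suppressed at year 3, R have prior confirmed rebound, and B have both. The headline is S/n. Counting rebound as failure gives (S - B)/n. The difference, B/n, cannot be negative, so the direction is fixed. The SAP reports S and R but not B. Even if both are reported on the same participants, they give only max(0, R + S - n) ≤ B ≤ min(R, S).

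As an illustration, take n = 158 and S = 142 (0.90 × 158 = 142.2). R is an assumption, because neither document gives a rebound rate.

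| R (assumed) | R + S - n | Range of B | Range of B/n, points |
|---|---|---|---|
| 2 | -14 | 0-2 | 0-1.3 |
| 3 | -13 | 0-3 | 0-1.9 |
| 5 | -11 | 0-5 | 0-3.2 |
| 8 | -8 | 0-8 | 0-5.1 |

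In each row the reported totals fit anything from no overlap to complete overlap. Only the cross-tabulation supplies B.

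**The case against.** The best defence is that the SAP did not create the gap. The heading of Protocol 3.4.2 speaks of analysis at each year, which favours separate proportions, and Protocol 3.5 sizes the study on one proportion at the end of three years. On that reading the protocol's own year-3 figure treats an earlier rebounder as sustained. Even the joint reading misses rebound between assessments. A reader might infer that moving to year 3 is what lets rebounders through; the documents do not establish that. This part of the defence stands.

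It also stands that the information is demoted and not lost. Years 1 and 2 are still reported, as are cumulative rebound and a composite that adds switches for virologic failure or intolerance. The study is descriptive only (Protocol 3.6), so no error rate or decision rule depends on which year is called primary.

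Making absence of rebound part of the primary definition would be open to challenge. It appears in neither document's primary endpoint, and it mixes thresholds: someone at 50-199 throughout years 1 and 2 would fail the below-50 rule then, yet pass the rebound condition.

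A reader might also infer that the change was prompted by results, since SAP version 1.0 dates from July 2023 and Amendment 1 shows sites already enrolling in December 2018. Nothing in the documents supports that. The timing is only a reason to write the rationale down.

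The defence does not answer the unexplained difference between the documents, the label, or the missing link between rebound and year-3 status.

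**Conclusion.** The point holds in limited form. The SAP reduces the primary time points to year 3 without a stated reason. What it calls sustained suppression is status at the assessment nearest day 1095, with a second value where the first is 50-200 copies/mL. Earlier confirmed rebound does not count against a participant who is still on treatment and on study and is below 50 at year 3. Whether the protocol shares this gap depends on a reading it does not settle: with separate proportions its year-3 figure has the same gap, and with a joint criterion the gap is smaller but not closed.

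The size cannot be determined, because neither document gives the share who rebound and then re-suppress on treatment. That share may be small, since those who switched or left the study are not in this group. The direction is certain: compared with a count that treats rebound as failure, the headline can only be higher. It would go beyond the documents to say that the result is materially wrong. They support saying that the label claims more than is measured and that the planned tables cannot show by how much.

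**What to change.** - Restore years 1, 2 and 3 as the primary time points, reported together as in Protocol 3.4.1, and state whether they are joint or separate. Otherwise keep year 3 alone and give the reason in the SAP. Either way, bring SAP 11.1.1, 11.3.1 and 11.3.2 into line.
- Keep the protocol's definition of success. Add a sensitivity analysis, specified before database lock, in which any confirmed rebound (two consecutive values of at least 200 copies/mL) since therapy start counts as not sustained.
- Cross-tabulate year-3 status by prior confirmed rebound on the same participants.
- Label the year-3 figure as suppression at year 3.

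The cost is SAP wording, one table and one additional analysis. Protocol 3.3.1 already asks sites to document viral load results, including re-tests outside visits, so no new data are needed. The downside is that the sensitivity figure may be slightly lower than the headline.

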### 11.3.2 Secondary Endpoints (EPs) (analyzed at years 1, 2 and 3 follow-up, unless otherwise stated)

- Primary endpoint is the proportion of participants with sustained virologic suppression, defined as HIV-RNA <50 copies/mL or if between 50-200 copies/mL with a subsequent next available measurement\* (within 120 days) <50 copies/mL at years 1 and 2 follow-up
- Proportion of participants with HIV-RNA <50 copies/mL at years 1, 2 and 3 follow-up
- Proportion of participants with low level viremia, defined as a HIV-RNA measurement ≥50 copies/mL and <200 copies/mL at years 1, 2 and 3 follow-up
- Proportion of participants with virologic rebound, defined as two consecutive HIV-RNA measurements ≥200 copies/mL from baseline until year 3 follow-up
- Proportion of participants with two consecutive measurements of ≥200 copies/mL, or treatment switch due to virologic failure or due to intolerance as determined at the discretion of the physician from baseline until year 3 follow-up
- Number of HIV monitoring measures (HIV-RNA measurements) [normalized to participant years] from baseline until year 3 follow-up
- Number and frequency of serious adverse events (SAEs) from baseline until year 3 follow-up [normalized to participant years] (see 11.3.10)
- Number and frequency of adverse drug reactions (ADRs) from baseline until year 3 follow-up [normalized to participant years] (see 11.3.10)
- Adherence to therapy [refers to missed monthly doses] at years 1, 2 and 3 follow-up (see 11.3.4)
- Change in lipid laboratory values at years 1, 2 and 3 follow-up (see 11.3.8.3)
- Change in treatment satisfaction [HIV Treatment Satisfaction questionnaire] at years 1, 2 and 3 follow-up (see 11.3.12.2)
- Change in symptom distress [HIV Symptom Distress Module questionnaire] at years 1, 2 and 3 follow-up (see 11.3.12.1)
- Reason for switch to DTG+RPV (see 11.3.5)
- Referral to other medical specialist from baseline until year 3 follow-up (see 11.3.7)
- Proportion of participants with resistance testing from baseline until year 3 follow-up
- Listing of detected resistance-associated mutations from baseline until year 3 follow-up
  - Listing of new (emerging) resistance-associated mutations, incl. resistance-associated mutations detected prior to treatment with DTG+RPV and last HIV-RNA

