3.4.2 Secondary Endpoints [analyzed at year 1, 2, 3 unless otherwise stated]

- Proportion of patients with low level viremia, defined as a VL measurement >50 - <200 c/ml
- Proportion of patients with VL >50 c/ml with emergent resistance mutations (if available)
- Proportion of patients with virologic rebound, defined as two consecutive VL measurements \geq 200 c/ml
- Proportion of patients with two consecutive measurements of \geq 200 c/ml, or treatment switch due to VF or due to intolerance as determined at the discretion of the physician
- Proportion of patients VL <50 c/ml
- Number of monitoring measures [normalized to patient years]
- Number and frequency of serious adverse events (SAEs) [normalized to patient years]
- Number and frequency of adverse drug reactions (ADRs) [normalized to patient years]
- Adherence to therapy [refers to missed monthly doses]
- Change in lipid laboratory values

- Change in treatment satisfaction [HIV Treatment Satisfaction questionnaire]
- Change in symptom distress [HIV Symptom Distress Module questionnaire]
- Reason for switch to Juluca

[* Any subsequent measurement will be accepted as a consecutive measurement as long as measured no later than 120 days after the initial measurement. If no subsequent VL measurement is performed within 120 days this is scored as a confirmed VL.]

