## **8 Analysis population, analyses sets**

### **8.1 Modified Full Analysis Set**

After closure of the database, all analyses will be based on the modified Full Analysis Set (mFAS) defined as follows:

- all participants of the FAS without
  - violation of in- or exclusion criteria (screening failures)major protocol violations (see 9)
- participants with protocol deviations may be excluded upon decision of the data review meeting.

The decision on the mFAS set will be made during the data review meeting prior to database lock.

A listing of all protocol violations and deviations will be produced, including the assessment major/minor and the procedure/consequence which followed.

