### **8.2 Effectiveness Set**

Following the primary endpoint, the effectiveness set comprises all participants of the mFAS except for

- participants lost to follow up (irrespective of last HIV-RNA level)
- participants on drug but without HIV-RNA in time window.

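### Rebound, and rebound or switch for failure/intolerance, are summarised over follow-up only as crude proportions; with up to 30% dropout planned for, a supplementary cumulative incidence would be a cheap improvement

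*SAP*

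**What the plan says.** SAP 11.3.2 has two items that summarise loss of suppression over the whole of follow-up. The first is rebound alone: "Proportion of participants with virologic rebound, defined as two consecutive HIV-RNA measurements ≥200 copies/mL from baseline until year 3 follow-up". The second is a composite that adds treatment switches, judged by the physician, over the same period: "Proportion of participants with two consecutive measurements of ≥200 copies/mL, or treatment switch due to virologic failure or due to intolerance".

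The other virologic proportions in SAP 11.3.1 and 11.3.2 (sustained suppression, HIV-RNA below 50, low-level viremia) are read in the yearly windows of SAP 10.2. Resistance testing and mutation listings also run from baseline to year 3, but they do not estimate the risk of losing suppression. SAP 11.3.5 reports the proportion who discontinue, their reasons, and a listing of last HIV-RNA for virologic discontinuations.

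On denominators, SAP 8.1 states that "all analyses will be based on the modified Full Analysis Set (mFAS"). SAP 8.2 defines an Effectiveness Set that follows the primary endpoint and leaves out "participants lost to follow up (irrespective of last HIV-RNA level"). SAP 10.3 bases categorical proportions on the non-missing sample size and, apart from the HIVTSQs score, allows no imputation. No section names a censoring rule, a Kaplan-Meier estimate or a cumulative incidence for loss of suppression.

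Protocol 3.4.2 also defines the first item as "Proportion of patients with virologic rebound, defined as two consecutive VL measurements" at or above 200 c/ml, but its heading sets the analysis at years 1, 2 and 3 unless stated otherwise, and nothing else is stated for rebound or the composite. The SAP pools both over the whole period.

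**The concern.** The primary objective is sustainability of suppression, and these two items are the only ones that cover the time between the yearly windows. Protocol 3.5 and SAP 7.2 plan for up to 30% dropout over 3 years. Someone who leaves at month 8 without an event was at risk for 8 months, yet in an mFAS proportion counts the same as someone observed event-free for 36. That proportion is the share in whom an event was seen. It equals the 3-year risk only if nobody is censored. A reader who takes it as the 3-year risk would read it too low by an amount that depends on how many leave, when, and why. Pooling also loses the yearly timing that the protocol gives.

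**Working it through.** **The plan's own figures.** With 90% efficacy, 95% confidence and total width 0.10, the smallest n whose exact (Clopper-Pearson) interval is narrow enough is 158 (width 0.0997). Then 158/0.70 = 225.7, so 226. Both stated numbers reproduce. They concern the primary proportion; the documents give no figure for rebound.

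**Inputs.**
- Dropout d = 0.30, the planned maximum (Protocol 3.5, SAP 7.2).
- N = 226 (same sections).
- True 3-year risk R: not in the documents. Assumed 2%, 5% and 10%.
- Assumed: leaving spread evenly over 3 years and independent of outcome; events spread evenly over time.

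**1. mFAS, event-free leavers as non-events.** A leaver is observed on average for half the period, so the expected proportion is (1−d)R + dR/2 = R(1−d/2) = 0.85R.
- 2% → 1.70% (shift 0.3 points, or 0.003 × 226 = 0.7 of a participant)
- 5% → 4.25% (0.75 points)
- 10% → 8.5% (1.5 points)

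The sampling SD at N=226 is √(0.0425×0.9575/226) = 1.3 points and √(0.085×0.915/226) = 1.9 points for the last two, so the shift is below one SD. At d = 0.10 the factor is 0.95: 4.75% and 9.5%.

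**2. Timing of dropout.** If all 30% left at month 6, the factor is 0.7 + 0.3×6/36 = 0.75. At month 30 it is 0.7 + 0.3×30/36 = 0.95.

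**3. The reading left open by the non-missing rule.** If event-free leavers were treated as missing but observed events kept, the proportion would be 0.85R / [0.85R + 0.7(1−R)].
- 5%: 0.0425/(0.0425 + 0.665) = 6.0%
- 10%: 0.085/(0.085 + 0.63) = 11.9%

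The error would then run the other way.

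**4. Leavers with a competing event.** If a share c of leavers stop or switch DTG+RPV and the rest are censored, the cumulative incidence of rebound is R × [1−0.7^(1+c)] / [0.3(1+c)].
- c = 0.25: factor 0.959, giving 4.8% and 9.6% for R = 5% and 10%
- c = 0.50: factor 0.921, giving 4.6% and 9.2%
- c = 1: factor 0.85, giving 4.25% and 8.5%, the same as the mFAS proportion

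The gap therefore shrinks to zero as c goes to 1. The documents do not give c.

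**5. Composite.** Switches for failure or intolerance are events here, so less follow-up is lost. With an assumed 20% independent loss for other reasons, the factor is 1 − 0.20/2 = 0.90: 10% reads 9.0% and 15% reads 13.5%.

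**6. Informative leaving.** Protocol 6.2.3 has patients with more than 28 days of non-adherence withdrawn. If leavers' rebound rate doubled after exit (an assumption), the true risk would be 0.7R + 0.3(R/2 + 2R/2) = 1.15R, or 5.75% at R = 5%. The mFAS proportion is 4.25% and an estimate with independent censoring gives 5.0%. It recovers 0.75 of the 1.5 points, about half.

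**The case against.** The protocol defines both endpoints as proportions, Protocol 3.6 makes the study purely descriptive, and an observed share of the enrolled set is a legitimate description. SAP 11.3.5 shows how many left and why. The shift is small, rests on assumed risks, and uses a maximum dropout rate. An R of 10% equals the whole non-suppressed share implied by the 90% efficacy assumption. All of this stands, and it limits the weight of the point. It does not remove it, because a cumulative incidence is also descriptive and the data for it are already collected.

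Four stronger readings are tempting but not supported.

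- *There is no rule for early leavers.* SAP 8.1 puts all analyses on the mFAS without exception. The only doubt left is whether an event-free leaver counts as non-missing under SAP 10.3.
- *Participants lost to follow-up are removed.* The Effectiveness Set is tied to the primary endpoint and is not assigned to these items.
- *An unrepeated value of 200 or more has no rule.* The SAP's asterisk is on sustained suppression only, and its footnote reads "If no subsequent HIV-RNA measurement is performed within 120 days this is scored as a confirmed HIV-RNA ≥200 copies/mL". But the protocol prints its footnote ("If no subsequent VL measurement is performed within 120 days this is scored as a confirmed VL") under the secondary list, where rebound and the composite are the items that use consecutive values. It can fairly be read as covering them, so a confirming sentence is enough.
- *The list contradicts itself because other items use person-time.* "Number of HIV monitoring measures (HIV-RNA measurements) [normalized to participant years] from baseline until year 3 follow-up", like the SAE and ADR counts, concerns repeatable events. Rebound is a once-per-participant outcome, so treating it differently is a choice and not an inconsistency.

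**Conclusion.** The point holds as an optional improvement. Under the natural mFAS reading, the two whole-follow-up proportions understate the 3-year risk when leaving is independent of outcome. With even 30% dropout the understatement is about 15% in relative terms: 0.3, 0.75 and 1.5 points at assumed risks of 2%, 5% and 10%. It is smaller with less or later dropout, larger with early dropout, and zero if every leaver has a competing event. Risks, timing, independence and the share of competing events are assumptions. A reader might infer that the planned results would be wrong or misleading. The documents do not support that: the proportions are valid as observed shares, and the shift at 5% and 10% is below one sampling SD.

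**What to change.** In SAP 11.3.2:

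- Keep both proportions. State that the denominator is the mFAS, that event-free leavers stay in it, and that events seen before loss count.
- Add, as supplementary descriptive estimates in the mFAS, the cumulative incidence (Aalen-Johansen) of each endpoint at years 1, 2 and 3, with 95% CIs and numbers at risk. This also restores the protocol's yearly timing.
- For both, censor loss to follow-up and administrative exit. For rebound alone, treat any stop or switch of DTG+RPV, and death, as competing events. For the composite, count a switch for virologic failure or intolerance as an event, and treat stops or switches for other reasons, and death, as competing.
- State the event date (for example, the first of the two values) and follow participants through the discontinuation record, so that a switch after the last HIV-RNA still counts.
- Confirm that the 120-day rule applies to an unrepeated value of 200 or more, and report how many participants this affects.
- Report censoring reasons, since withdrawal for non-adherence may make censoring informative and the estimate would then correct only part of the bias.

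Viral-load results including retests (Protocol 3.3.1), date and reason of discontinuation, and subsequent ART (SAP 7.4, 11.3.5) are already collected. The cost is SAP text, some Stata code and reliance on a censoring assumption. The primary endpoint is unchanged.

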2.2 Secondary

- Gain an understanding of the major relevant patient populations for Juluca in Germany, in terms of patient characteristics and history
- Describe real-life efficacy profile of Juluca
- Describe real-life tolerability profile of Juluca as measured by discontinuation rates due to adverse drug reactions (ADRs) and overall number of serious adverse events (SAE)
- Analyze the development of viral resistance by evaluating available resistance data in case of virologic failure
- Describe impact on lipid metabolism
- Evaluate medical need for a substance and/or class sparing treatment regimen by assessing the reason for switching to Juluca
- Describe patients' treatment satisfaction and symptom distress based on validated questionnaires
- Evaluate number of monitoring measures and referrals to other specialists

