## 7.4 Flow chart

For details see 11.2 and 11.3.

Forms	Visit	Enrollment visit	Baseline visit (=last visit before start of therapy with DTG+RPV)	(Routine-based) Follow-up visits until end of study	Study discontinuation	Independent of visits, continuous reporting
Informed consent		X				
In-, exclusion criteria		X				
Date of start with JULUCA			X			
Demography			X			
HIV/ART history			X			
Anamnesis (drug adherence, pregnancy, vital signs incl. weight)			X	X	X	
Laboratory parameters (hematology, metabolic parameters and clinical chemistry, transaminases and lipids)			X	X	X	
Comedication			X	X	X	
Comorbidities			X	X	X	
Referrals to another medical specialist			X	X	X	
Resistance mutation testing			X	X	X	
HIV TSQ			X	X	X	
HIV SDM			X	X	X	
Date & reason of study discontinuation					X	
Post ART					X	
ADR/SAE						X
HIV-related characteristics (laboratory parameters)						X

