### 11.3.7 Referrals to another medical specialists

- Percentage of participants referred to another medical specialists (all referrals from baseline until year 3 follow-up)

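### Referrals are reported only as the percentage of participants referred, which does not give the number the objective asks for; monitoring is narrowed to HIV-RNA tests without a stated reason

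*SAP*

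**What the plan says.** Protocol 2.2 gives the objective as "Evaluate number of monitoring measures and referrals to other specialists", and SAP 6.2 carries it over unchanged.

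For monitoring, the endpoint in Protocol 3.4.2 is "Number of monitoring measures [normalized to patient years", closed by a bracket. The protocol does not define the term or restrict it to viral load. SAP 11.3.2 replaces it with "Number of HIV monitoring measures (HIV-RNA measurements) [normalized to participant years] from baseline until year 3 follow-up".

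For referrals, Protocol 3.4.2 lists no endpoint. SAP 11.3.2 adds one, "Referral to other medical specialist from baseline until year 3 follow-up (see 11.3.7"), without naming a statistic. SAP 11.3.7 names the only one: "Percentage of participants referred to another medical specialists (all referrals from baseline until year 3 follow-up").

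The flow chart in SAP 7.4 has a row for "Referrals to another medical specialist" and a row for "Laboratory parameters (hematology, metabolic parameters and clinical chemistry, transaminases and lipids"), both ticked at baseline, follow-up and discontinuation. Resistance testing is collected at the same points and is analysed as "Proportion of participants with resistance testing from baseline until year 3 follow-up", plus listings.

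**The concern.** The objective asks for a number, and the planned referral statistic is a share of people. A participant referred once and a participant referred ten times count the same. Someone who leaves early also has less time to be referred, so the share depends on how long people were observed as well as on how often referrals occur. The same list in SAP 11.3.2 normalizes HIV-RNA tests, SAEs and ADRs to participant years, so referrals are an unexplained exception.

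On monitoring, the SAP uses a narrower term than the protocol and does not say why. Hematology, chemistry, lipid, CD4, urine and resistance results are collected or analysed, but no count per participant-year is planned for any of them.

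At stake is whether the report can answer one of its own secondary objectives. The referral part would not be answered as worded, and the monitoring part would be answered for viral load only.

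**Working it through.** **Inputs.** The plan gives no figure for referrals or monitoring, so there is none to reproduce on this point. Three numbers are borrowed from Protocol 3.5 and 3.1: 158 participants at the end of the study, a maximum dropout of 30%, and about 3 years of follow-up. The first two are consistent with the plan's recruitment figure: 158 / 0.70 = 225.7, hence 226. The referral rates, the shares referred, the count distributions and the leaving times below are assumptions.

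**Step 1: does the percentage give the number?** Take 158 participants followed for 3 full years, which is 158 × 3 = 474 participant-years. Let p be the share ever referred and m the mean number of referrals per person.

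- Poisson counts: m = −ln(1 − p).
- Negative binomial counts with dispersion k: m = k × [(1 − p)^(−1/k) − 1]. Here k = 0.25 represents strong clustering of referrals in a few people.

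| Share ever referred | Distribution | m | Referrals (158 × m) | Per 100 participant-years |
|---|---|---|---|---|
| 30% | Poisson | 0.357 | about 56 | 11.9 |
| 30% | Negative binomial, k = 0.25 | 0.791 | about 125 | 26.4 |
| 50% | Poisson | 0.693 | about 110 | 23.1 |
| 50% | Negative binomial, k = 0.25 | 3.75 | about 592 | 125 |

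The same percentage fits counts that differ 2.2-fold at 30% (26.4 / 11.9) and 5.4-fold at 50% (125 / 23.1). It does not determine the number.

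**Step 2: does the percentage depend on follow-up?** With a constant Poisson rate r per year, the share ever referred by time t is 1 − exp(−r t). If 30% leave at 18 months and 70% stay 3 years, the share falls, compared with full follow-up, by

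0.3 × [exp(−1.5 r) − exp(−3 r)].

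| r per year | Full follow-up | 30% leave at 18 months | Fall (points) |
|---|---|---|---|
| 0.1 | 25.9% | 22.3% | 3.6 |
| 0.3 | 59.3% | 52.4% | 6.9 |
| 0.46 | 75.0% | 67.5% | 7.5 |
| 1.0 | 95.0% | 89.8% | 5.2 |

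The maximum occurs where exp(−1.5 r) = 0.5, that is r = ln 2 / 1.5 = 0.46, and equals 0.3 × (0.5 − 0.25) = 0.075. Over rates of 0.1 to 1.0 the fall is therefore about 4 to 7.5 points. Earlier leaving widens it. At r = 0.3 with all leavers at 12 months, it is 0.3 × [exp(−0.3) − exp(−0.9)] = 0.3 × (0.741 − 0.407) = 10.0 points. With no dropout it is zero.

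**Step 3: are early leavers in this analysis?** SAP 8.1 bases all analyses on the mFAS. The exclusion of participants lost to follow-up in SAP 8.2 belongs to the effectiveness set, which is built for the primary endpoint. Nothing in 11.3.7 restricts the referral percentage to people with full follow-up.

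**Step 4: what is counted as monitoring?** Only HIV-RNA tests get a rate. The year 1, 2 and 3 tables for other laboratory values cannot supply one, because SAP 10.2 keeps the single assessment closest to each anniversary.

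**The case against.** The protocol never defines monitoring measures, and its section 4 leaves detailed methodology to the SAP. Restricting the count to HIV-RNA fits the primary objective of viral suppression and may be a deliberate operational definition. That stands. What remains is that the SAP gives no reason for a restriction the protocol wording does not contain.

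A reader might infer that monitoring is not estimated at all. It is: HIV-RNA tests are planned as a rate per participant-year. The SAP also reports the proportion with resistance testing, and SAP 10.3 gives the non-missing n for each continuous laboratory variable. These last two are not rates, but they carry some information.

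A reader might also infer that the HIV-RNA count merely restates the visit schedule, because follow-up every 2 to 4 months means 12/4 = 3 to 12/2 = 6 visits a year. The documents do not support this. Protocol 3.3.1 leaves visit frequency to the treating physician and has viral-load results documented even from contacts that are not study visits. The flow chart in SAP 7.4 puts HIV-related laboratory parameters in the column for continuous, visit-independent reporting. Viral load is, if anything, less tied to visits than the general laboratory panel.

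Finally, the SAP did not replace a planned referral count with a percentage. The protocol's endpoint list has no referral endpoint, so the gap begins there, and the SAP adds something the protocol lacked. The statistic it adds still does not answer the objective. The words in parentheses in 11.3.7 fix the period and which referrals qualify; they do not turn the output into a count.

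**Conclusion.** The point holds for referrals. The objective is a number, the plan yields a percentage, and the percentage neither determines the number nor allows for unequal follow-up. On the illustrative assumptions (constant rate of 0.1 to 1.0 per participant-year, the maximum 30% dropout all at 18 months), shorter follow-up alone lowers it by about 4 to 7.5 points. The true figure is unknown, since the documents give neither referral rates nor leaving times.

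For monitoring the point is narrower: only the viral-load part is estimated as a rate, and the restriction is unexplained. It would go too far to say that the percentage could never be set beside other cohorts; the documents neither show nor exclude that.

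The matter is minor. It concerns a secondary descriptive objective and changes nothing in the primary endpoint or the sample size.

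**What to change.** **Referrals (SAP 11.3.2 and 11.3.7).** Keep the percentage and add the total number of referrals and the rate per participant-year. Define person-time as running from therapy start to the year 3 visit, or to the last on-study contact if that is earlier. The period in SAP 10.2.1 ends at the year 3 visit and gives no end date for people who leave before it. The flow chart places the baseline visit before therapy start, so the referral count should start at therapy start to match the person-time. Break the figures down by specialty only if the eCRF records it; the documents show only the form title.

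**Monitoring (SAP 11.3.2).** Either state that HIV-RNA testing is the intended definition of monitoring measures, with the reason, or add counts per participant-year for the other test types already recorded (the laboratory panels and resistance tests in SAP 7.4, CD4 in 11.3.3, urine in 11.3.8.6), keeping HIV-RNA as one row.

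**Cost.** SAP wording, an extra row or table, and a little more programming. The flow chart indicates that no new data collection is needed for referral counts, provided the form records each referral.
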